4.3. EXCLUSION CRITERIA

- Subject has not failed at least one courses of non-MTX chemotherapy or one course of non-MTX chemotherapy and chemoradiation for treating their SCCHN.
- Uncontrolled active infection.
- Current mucositis (> Grade 1).
- Pregnancy or nursing mother.
- Prior history of a cerebrovascular accident or hemorrhage.
- Congestive heart failure as defined by New York Heart Association class III or IV.
- Uncontrolled hypertension.
- Active psychiatric or mental illness making informed consent or careful clinical follow-up unlikely.
- Subjects who have previously been enrolled into this study and subsequently withdrew.
- Subject receiving other investigational agent(s).
- Any systemic immunosuppressive medication/therapy (eg, chemotherapy, steroids).
- Any significant systemic illness, unstable or severe medical condition(s) that could put the subject at risk during the study, interfere with outcome measures or affect compliance with the protocol procedures such as autoimmune disease, ie, any condition that compromises the immune system and/or intercurrent infection
- Known or suspected intolerance or hypersensitivity to the study materials [TK-112690 and/or excipients or closely related compounds].
- Subjects who have received radiation or chemotherapy within 4 weeks of projected enrollment.
- Subjects that have a history of poor compliance in clinical research studies.
- Subjects who have participated in any other investigative clinical trial in the past 4 weeks.

4.4. WAIVERS

No waivers can be granted for inclusion in the study.

5.0. STUDY TREATMENT

5.1. DESCRIPTION OF TREATMENT

5.1.1. Study Drug

METREXASSISTTM (TK-112690 for Injection) is a clear, sterile, neutral, aqueous solution containing 100 mg/mL TK-112690. TK-112690 is a water soluble anhydrouridine that inhibits uridine phosphorylase. METREXASSISTTM is an aqueous 5 mL solution, pH 7.4 in 50 mM sodium phosphate,

packaged in a 10 mL flint glass vial with an elastomeric stopper held in place by an aluminum seal and flip-off cap. $METREXASSIST^{TM}$ is supplied for administration by continuous iv infusion over one hour in a final of volume of 250 mL Saline for Injection (USP). $METREXASSIST^{TM}$ is to be re-suspended for infusion in Saline for Injection (USP). The vials must be stored frozen (-15 to -25°C).. Once opened, solution for infusion containing must be used within 8 hours of preparation.

5.1.2. Study Drug Placebo

10 mL glass vials of isotonic saline equipped with an elastomeric stopper held in place by an aluminum seal and flip-off cap.

5.1.3. MTX

MTX drug product traditionally used at the clinical site,

5.1.4. Nutritional Supplement

The nutritional supplement containing uridine monophosphate (Fortasyn ConnectTM / SouvenaidTM) is a commercial, over the counter, product available from Nutricia NV. The supplement will be given to all dosed patients one hour prior to the TK-112690/placebo infusion (2 hours before the MTX infusion).

5.2. STUDY THERAPY ADMINISTRATION

The study therapy will be administered as an infusion via a peripheral vein in the forearm delivered using a catheter. This access vein for the infusion must not be used for blood sampling. Replacement of the intravenous catheter will be done according to local practice and the discretion of PI or designee, e.g., in the event of phlebitis. If a catheter is replaced, it should be flushed with saline prior to removal unless there are signs of phlebitis. TK-112690/placebo will initially be administered as a one-hour infusion. In case of immediate adverse reaction to the infusion, please follow management of reaction (Appendix 4: Infusion Reaction Criteria).

Epinephrine (1:1000) for subcutaneous injection, diphenhydramine (12.5 mg to 50 mg) for iv injection, and any other medications and resuscitation equipment for the emergency management of anaphylactic reactions must be available in the room where the infusions are being performed.

All patients will be evaluated at a follow-up visit on Day 1 of Week 6 post after initial drug treatments.

METREXASSISTTM (TK-112690 for Injection) should be prepared for infusion by a healthcare professional using aseptic technique. METREXASSISTTM will be diluted into 250 mL of 0.9% sodium chloride in a iv bag/bottle. Please refer to **Appendix 3** for the directions on how to calculate and dilute for the different doses to be administered to the subjects.

For the placebo will be prepared as described above for the TK-112690 except isotonic saline in 10 mL glass vials will be substituted for the 10 mL METREXASSISTTM vials.

Dosing will be calculated on a mg/kg basis and rounded to the closest 10 mg. The TK-112690/placebo dose will be 45 mg/kg.

5.3. SELECTION AND TIMING OF DOSE FOR EACH SUBJECT

Dosage will be administered to enrolled subjects as defined in the protocol \pm one day

5.4. PACKAGING AND LABELING

METREXASSISTTM and placebo will be supplied by Tosk in labeled, sealed 10 ml vials.

The vials will be labeled as follows:

The boxes will be labeled as follows:

TK-112690 Injection, 100 mglmL Shipper contents: 24 vials Store -25 to -15°C (-13 to 5°F) In a freezer. Caution: New Drug. Limited by United States law to investigational use Stability periods: Acc stb: T1, T2, T3,T6. Lt stb: T3, T6, T9,T12,T18,T24.

5.5. BLIND\CODE BREAK

Phase 2a is a partially blinded study. The patient and investigator will be blinded as to whether TK-112690 or placebo is administered, and the CRO, Sponsor, and site pharmacist (unblinded) will know whether TK-112690 or placebo, was administered. The Pharmacist will be receiving all the vials from CRO, on randomization to a particular group the unblinded pharmacist will take the IP\Placebo and mask it with a white sticker so that the blind is maintained at all times. At the request of the investigator, the code can be broken. A Subject's treatment assignment will not be broken until the end of the study, unless medical treatment of the subject depends on knowing the study treatment the subject received. In the event that the blind needs to be broken because of a medical emergency, the investigator may unblind an individual subject's treatment allocation. As soon as possible, the investigator should first contact the medical monitor to discuss the medical emergency and the reason for revealing the actual treatment received by that subject. It should be documented in the case record form. For unblinding, investigator may also ask the medical monitor, who will in turn ask the unblinded statistician to provide the code to the investigator for the particular subject. The date on which the code was broken, together with the identity of the person responsible, must also be documented. When the investigator unblinds a patient treatment for emergency reasons, he/she must note the date, time, and reason for doing it and record this information in the source notes.

5.6. STORAGE AND ACCOUNTABILITY

All study therapy must be kept in a secure place under adequate storage conditions. The TK-112690infusion concentrate must be frozen (-20°C \pm 5°C) and protected from light. Placebo must be stored between 15 °C to 30 °C.

The PI has overall responsibility for ensuring that study therapy is stored in a safe limited access location under the specified appropriate storage conditions. Limited responsibility may be delegated to a nominated pharmacy representative, but this delegation must be documented.

Study therapy will be dispensed by the pharmacist or designated member of the study team. The PI or designee will record dispensing of the study medication on a study medication accountability record. These records should include dates, quantities, batch/serial numbers, updated expiration dates (if applicable), and the unique code number assigned to the investigational product and trial subject. This record will be made available to clinical monitoring personnel for the purpose of accounting for the

clinical study medication supply. A study medication supply inspection for inventory purposes and assurance of proper storage will be conducted as necessary. Any significant discrepancy will be recorded and reported to the sponsor and a plan for resolution will be documented.

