6.6. DISPENSING STUDY DRUG

Study drugs must be used only as directed in the protocol. The PI will be provided with forms to enable accurate, written records of all medication received from Tosk. These records will be kept by the PI or pharmacist/nominated person. The PI or pharmacist/nominated person will also keep accurate records of the quantities dispensed and used of the investigational product.

At the end of the study, all unused trial medication (ie, vials) will be returned by the pharmacist/ nominated person to a nominated contractor on behalf of Tosk. All certificates of delivery and returns must be signed by the pharmacist/nominated person. Based on entries in the drug accountability forms, at the end of the trial, it must be possible to reconcile delivery records with those of usage and returned stocks. All study medication must be accounted for and all discrepancies documented appropriately.

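### Sections 5.6 and 6.6 let the blinded investigator hold subject-linked batch records and oversee product-specific storage, and nothing keeps the mucositis scorer away from either.

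*Combined protocol and SAP*

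**What the plan says.** Sections 3.5 and 5.5 of the combined protocol and SAP set the blind. Section 5.5 states: "The patient and investigator will be blinded as to whether TK-112690 or placebo is administered". The CRO, the sponsor and the site pharmacist know the assignment.

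Section 5.6 (Storage and Accountability) sets the handling rules:

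- Storage conditions: "The TK-112690infusion concentrate must be frozen" (−20 ± 5 °C), whereas "Placebo must be stored between" 15 °C and 30 °C.
- Responsibility: "The PI has overall responsibility for ensuring that study therapy is stored in a safe limited access location". On delegation: "Limited responsibility may be delegated to a nominated pharmacy representative, but this delegation must be documented".
- Dispensing: by the pharmacist or by another designated team member.
- Recording: "The PI or designee will record dispensing of the study medication on a study medication accountability record".
- Content: "These records should include dates, quantities, batch/serial numbers, updated expiration dates (if applicable"), followed by a unique code assigned to the product and to the trial subject.

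Section 6.6 (Dispensing Study Drug) gives the PI the forms for logging medication received from the sponsor and adds: "These records will be kept by the PI or pharmacist/nominated person". The same people may keep the records of quantities dispensed and used.

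The separate section on mucositis assessment, also numbered 6.6, describes scoring in the passive voice and does not say who does it.

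**The concern.** A blind protects an endpoint only if the people who grade it cannot learn the arm. Here the role that is meant to be blinded is also one of the roles allowed to keep the log linking each subject to a batch, and it carries responsibility for stock whose storage conditions show which product it is. Section 3.1 makes scores on four mucositis scales the efficacy outcome. WHO grade, CTCAE grade and the OMAS erythema rating (severe or not severe) all need an examiner's judgement.

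Scoring is not the only route to the results. Under section 9.3 the PI records the severity of adverse events and their relationship to study drug. Section 3.3.1 leaves treatment of stomatitis to the PI's discretion, and section 8.2 allows discretionary withdrawal. Withdrawal can affect who reaches the four doses that section 10.2.1 requires for the efficacy population. The Rationale section says that the partial blind is there to make the results more reliable, and section 10.1.1 intends to use these data to size the next study. Bias introduced here would carry forward.

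**Working it through.** There is no figure in the plan to reproduce and no arithmetic to run: section 10.1.1 says that the sample size does not rest on a statistical calculation. The check sets the sections side by side.

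1. **Who may know the arm.** Sections 3.5 and 5.5: at the site, only the pharmacist. The investigator may not.

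2. **Who may hold the records.** Section 5.6: the PI or a designee records dispensing. Section 6.6 (Dispensing Study Drug): the PI, the pharmacist or a nominated person keeps the receipt and usage records. Delegation of storage duties to pharmacy is optional and limited. So an investigator who personally keeps these records complies with 5.6 and 6.6. Section 6.6 also sits awkwardly with 5.5, where it is the pharmacist who receives all vials from the CRO.

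3. **Does the record identify the arm?** The log links subject to batch or serial number. Active and placebo are different products, one a 100 mg/mL solution of TK-112690 and the other isotonic saline. If batch numbers are product-specific, the log sorts subjects by arm, and recognising one batch classifies every subject entered against it. The documents do not give the numbering scheme, so product-specific batches are an assumption.

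4. **Does storage identify the arm?** Stock in the freezer is active and stock at room temperature is placebo. Anyone who sees where a subject's vials are taken from knows the arm, with no assumption about numbering. The box label shown in section 5.4 also names TK-112690 and specifies a freezer.

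5. **Do the masking steps cover this?** Section 3.5 has the CRO supply re-labelled vials. Section 5.5 has the pharmacist apply a white sticker once the subject is randomised. These are two different descriptions, and both act on the vial. Neither mentions the log, the batch number or the storage location. Section 3.5 also lets a designated person other than the pharmacist prepare the infusion, and that person is not on its list of unblinded roles.

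6. **Is the scorer separated?** The scorer is unnamed. No section bars the PI, or whoever scores, from the accountability records or the storage area.

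Taken together, a site can follow 5.6 and 6.6 to the letter and still break the blind set by 3.5 and 5.5.

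**The case against.** The strongest defence is that the text can be followed without any leak. Section 11.0 defines PI to include staff designated for a task, so the unblinded pharmacist can do everything that 5.6 and 6.6 ask. Section 5.5 already has the pharmacist receive, select and mask the vials, and specific blinding language can be read as governing generic accountability language. Overall responsibility for storage does not oblige the PI to look at which subject's vial came from where.

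This stands as far as it goes: the leak is permitted, not ordered. It does not close the gap, because the compliant arrangement is left to each site and no section excludes the PI or scorers from the records.

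Four stronger readings are tempting and are not supported:

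- *The investigator is instructed to keep these records.* The wording is PI or designee, and PI includes designated staff.
- *Active and placebo look different.* Sections 5.1.1 and 5.1.2 describe 10 mL glass vials with the same type of closure. The difference that the documents support is storage temperature and the active box label.
- *The PI scores mucositis.* No section says who does. One of the four scales, PROMS, is completed by the patient, who is given no role in these records.
- *A false-positive rate can be attached.* That needs an assumed bias and a significance test. The synopsis plans descriptive statistics for the mucositis scales, and section 10.1.1 calls the study exploratory and possibly not powered for significance.

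**Conclusion.** The point holds as an unresolved conflict between sections. Sections 5.6 and 6.6 (Dispensing Study Drug) allow the blinded PI, or a designated team member, to dispense study therapy, keep subject-linked batch and receipt records, and oversee storage that differs by product. Sections 3.5 and 5.5 require the investigator not to know the arm.

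The possible consequence is bias in the three clinician-graded scales and in discretionary decisions at the site, in a comparison of only 11 patients per arm. Its size cannot be derived from the documents. It depends on how sites delegate, on whether batch numbers identify the product, and on who scores. The log route rests on product-specific batches; the storage route does not. Sample size, alpha and power are unaffected. The change is worth making because it is cheap and removes a doubt about the efficacy scores that could not be settled after the trial.

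**What to change.** In sections 5.6 and 6.6 (Dispensing Study Drug):

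- Assign receipt, storage, dispensing and accountability records to the unblinded site pharmacist, or to a documented unblinded delegate who makes no subject assessments.
- State that the PI and everyone who scores mucositis have no access to these records until database lock, apart from the emergency code break already provided in 5.5.
- Have unblinded CRO staff check the records.

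The unblinded pharmacist and CRO already exist in the design, so the cost is a wording amendment and entries in the site delegation log.

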5.7. INVESTIGATIONAL PRODUCT RETENTION AT STUDY SITE AND DESTRUCTION

All study therapy required for completion of this study will be provided by Tosk (MetrexassistTM, placebo and the nutritional supplement,).

The recipient will acknowledge receipt of the drug indicating shipment content and condition. Damaged supplies will be replaced. Accurate records of all study drug dispensed, used, and returned will be maintained. At the conclusion of the trial, all unused and used vials of will be returned to the sponsor or designee. Alternately, drug may be destroyed on site as dictated by the standard operating procedures at the participating institution (if appropriate). Vials should only be destroyed or returned after drug accountability has been performed by the clinical research associate and all vials were accounted for. If there is an error or perceived error, vials should be returned to Tosk.

5.8. DURATION

Phase 2a:

Start Date:	First Quarter 2019
End of Recruitment:	3rd Quarter 2019
End of Treatment:	Fourth Quarter 2019

6.0. STUDY PROCEDURES

6.1. INFORMED CONSENT

All subjects are to give informed consent in accordance with the origins of the Declaration of Helsinki (Appendix 1) and CFR part 50. The informed consent form as well as any advertisements used to recruit patients must be approved by the IRB/IEC.

The subject will provide the sign/thumb impression on the Informed Consent Form (ICF) before she/he enters the study, ie, before screening blood samples, screening assessments or any other study-related activity. The subject will be given sufficient time to consider the study's implications before deciding whether to participate. The informed consent form as well as any advertisements used to recruit patients must be approved by the IRB/IEC. Participants must sign/thumb impression the IRB/IEC-approved informed consent form prior to participation in any study specific procedure. The participant must receive a copy of the signed and dated consent document. The original signed copy of the consent document must be retained in the research file.

Should there be any amendments to the final protocol, the subject must agree to sign/thumb impression the amended ICF indicating that they re-consent to participate in the trial.

6.2. SUBJECT IDENTIFICATION

6.2.1. Subject Registration

Prior to registration and any study-specific evaluations being performed, all subjects must have given written informed consent for the trial and must have completed the screening evaluations (see Section 7.1). Subjects must meet all of the eligibility requirements listed in Section 4.0.

6.2.2. Subject Number

When the subject has completed the screening process and enters into the trial, he/she will be assigned a unique subject number composed of a site identification number and unique subject identification sequence number. The subject number and the subject's initials will be used as identification for the whole duration of the study.

6.3. MEDICAL HISTORY

Medical history will be performed at screening and will establishing age, sex, race, history of smoking/alcohol consumption/drugs and including subject's disease history. The review of previous/ongoing medications should cover a period of time that is 180 days prior to enrollment.

6.4. PHYSICAL EXAMINATION

A complete physical examination will be conducted at screening, on Day 0, 24 and 48 hours post each TK-112690/placebo dosing and on Day 1 of Week 6. Physical examination will be performed by site personnel who are experienced and routinely conduct physical examinations.

6.5. VITAL SIGNS, WEIGHT DETERMINATIONS AND CARDIOVASCULAR ASSESSMENTS

Body temperature will be recorded by the oral, rectal or tympanic route at screening and during weekly visits. The same route should be used for all measurements, if possiblesupine blood pressure (systolic and diastolic), respiratory rate and pulse will be recorded at screening (defined as baseline) and at Day 0, and 24 and 48 hours post TK-112690 /placebo infusions as well as on Day 1 of Week6. The time of the measurements will be noted. All measurements will be made with the subject in the supine position. Blood pressure should be determined by cuff (manual or automated is acceptable, although the same method should be used throughout the study).

Weight will be determined concurrent with vital sign measurements.

A standard 12 lead ECG will be recorded at screening (defined as baseline) and at 24 post each TK-112690/placebo dosing. The PI will provide an overall judgment of the ECG.

6.6. DISPENSING STUDY DRUG

Study drugs must be used only as directed in the protocol. The PI will be provided with forms to enable accurate, written records of all medication received from Tosk. These records will be kept by the PI or pharmacist/nominated person. The PI or pharmacist/nominated person will also keep accurate records of the quantities dispensed and used of the investigational product.

At the end of the study, all unused trial medication (ie, vials) will be returned by the pharmacist/ nominated person to a nominated contractor on behalf of Tosk. All certificates of delivery and returns must be signed by the pharmacist/nominated person. Based on entries in the drug accountability forms, at the end of the trial, it must be possible to reconcile delivery records with those of usage and returned stocks. All study medication must be accounted for and all discrepancies documented appropriately.

6.7. CLINICAL LABORATORY TESTS

6.7.1. Laboratory Parameters

Nitrite pH

Besides the Central Laboratory Tests, an in-house (at site) CBC, Kidney function test, Liver function test will be performed to qualify the subject for dosing with MTX, .Coagulation: (prothrombin time, PT, and activated partial thromboplastin time, PTT,tests will be performed at the Local laboratory associated with the clinical site as per schedule of events.

Subjects will be in a seated or supine position during blood collection. Clinical laboratory tests to be performed are included in **Table 10**. **Table 10**. **Central Laboratory Tests**

Hematology:SerumHematocrit (Hct)Hemoglobin (Hb)Mean corpuscular hemoglobin concentration (MCHC)Mean corpuscular volume (MCV)Platelet countRed blood cell (RBC) countWhite blood cell (WBC) count with differential	Blood urea nitrogen (BUN) C-reactive protein Calcium (Ca) Chloride (Cl) Creatinine Creatinine kinase Direct bilirubin Total bilirubin Total cholesterol (non-fasting) Total protein Triglycerides (non-fasting) Uric acid Gamma-glutamyltransferase (GGT) Globulin Glucose (Random)
Urinalysis :(will be performed by dipstick) Appearance Color Glucose Protein Occult blood	

Urine human chorionic gonadotropin: Females of childbearing potential only

Coagulation:

- Prothrombin time (PT)
- Activated partial thromboplastin time (PTT)

The laboratory measurements of clinical chemistry, hematology and urinalysis will be performed during screening (defined as baseline), on Day 0 and at 24 and 48 hours post each initial infusion of TK-112690 or Placeboas well as on Day 1 of Week6.

All laboratory measurements will be performed at a central laboratory. The laboratory will provide the PI and Tosk with test results including units, relevant reference ranges and updates as necessary. Laboratory measurements can also be performed at local sites for medical or informational reasons However; these measurements will not be considered part of the study record.

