Title of the Study

A Phase 2a, Multi-center, Placebo-controlled, Randomized, Partially Blinded, Study of Infused METREXASSISTTM (Parenteral TK-112690) or MetrexassistTM Placebo Administered Along with Methotrexate Weekly for Four Consecutive Weeks to Patients with recurrent or residual SCCHN.

Principal Investigators Approximately 3

Study Centers Approximately 3

Clinical Phase

Phase 2a

Number of Subjects

The total number of individuals enrolled will be 22, 11 dosed TK-112690 and methotrexate and 11 patients dosed methotrexate and placebo. All patients will be dosed a nutritional supplement to assure adequate basal levels of uridine and uridine-related biochemicals.

Study Drug:TK-112690, an anhydrouridine inhibitor of uridine phosphorylase

Projected Subject Enrollment Duration

10 months

Objectives

Primary

Determine pilot efficacy of an iv infusion of TK-112690 to placebo as a mucositis preventive in subjects with locally advanced, residual, or recurrent or metastatic SCCHN scheduled to receive MTX as chemotherapy.

Secondary

Confirmation of the safety/tolerability of a continuous administered weekly for 4 weeks and lowering of plasma concentrations of surrogate markers of mucositis, e.g., CD40/CD40L, post TK-112690 in patients

suffering from local, advanced, residual or recurrent, metastatic SCCHN receiving sequential continuous iv infusions of TK-112690 and MTX or TK-112690 placebo and MTX.

Study Design

A Phase 2a, Multi-center, Placebo-controlled, Randomized, Partially Blinded, Study in Patients with recurrent or residual SCCHN.

Patients will receive MTX at a dose of 45 mg/m² administered weekly for **4 consecutive weeks** as an iv infusion along with a nutritional supplement containing uridine monophosphate (Fortasyn ConnectTM / SouvenaidTM, Nutricia NV) administered two hours before the MTX. One hour before the MTX treatment the patients will be administered the first infusion of the day of either TK-112690 or placebo depending on randomization infusion. Five hours after the MTX treatment the patients will be administered the second treatment of either TK-112690 or placebo depending on randomization. The TK-112690 dose will be 45 mg/kg.

- A total of 22 patients will be enrolled into one of 2 different dose groups: TK-112690 treated or placebo treated.
- Screening must be within 15 days of subject enrollment.
- Patients will remain for observation at the clinical site for a minimum of 25 hours post initial TK-112690 or placebo dose.

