7.1.1 Screening Visit

To be accomplished within 15 days of expected initial dosing and ONLY AFTER THE ICF IS SIGNED.

An Eligibility Screening Form (ESF) documenting the subject's fulfillment of the entry criteria for all subjects considered for the study is to be completed by the PI. Subjects who are considered for study entry, but who fail to meet the eligibility requirements, will also have an ESF completed with the reason for ineligibility. These subjects will not be entered into the trial database. The ESFs for subjects who fail to meet the eligibility criteria requirements should be kept in the files at the sites.

During this visit the following activities will be performed:

- Eligible subjects meeting the inclusion/exclusion criteria for this study will be asked to read, comprehend, and sign/thumb impression an informed consent form.
- The subject medical history and concomitant medication use will be recorded as well as a history of drug abuse, alcohol consumption, and tobacco use.
- Perform a urine screen for drugs of abuse.
- A complete physical examination will be performed assessing the following: Skin, eyes, ear, nose, throat, neck, thyroid, lungs, heart, abdomen, lymph nodes, extremities, and body weight.
- Vital signs and weight will be measured as well as an AE assessment.
- ECOG performance status (Section 20.2 Appendix 2)
- A pregnancy test will be performed on women of childbearing potential.
- A 12-lead ECG will be performed.
- The following laboratory test will be performed: hematological panel, infective agent panel, serum chemistry, coagulation and urinalysis (Laboratory tests, see **Table 10** for complete list of tests).
- Disease (tumor) assessment by CT scanning will be performed within 7 days post screening but before the first dosing.

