7.1.2 Day before start of study (Day 0)

Prior to study start, all subjects will undergo the following:

- Randomization
- Perform urine screen for drugs of abuse.
- A physical examination to update findings from the examination performed at screening.
- Perform vital sign and weight measurements.
- ECOG performance status.
- A pregnancy test will be performed on women of childbearing potential.
- Perform laboratory tests (hematology, chemistry, coagulation and urinalysis).
- Perform a mucositis assessment (Section 20.6, Appendix 6).

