10.3.2. Laboratory Data

The number and percentage of subjects with laboratory abnormalities at the screening visit and the final visit (or early withdrawal) will be tabulated.

Descriptive statistics (number of observations, mean, standard deviation, minimum, median and maximum values) will be calculated for clinical laboratory tests (hematology, serum chemistry, and urinalysis) at applicable visits.

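### The safety baseline for laboratory values and main vital signs is set at screening, up to 15 days before dosing, although the same measurements are repeated on Day 0

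*Combined protocol and SAP*

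**What the plan says.** **Baseline label.** Section 6.7.1 states that clinical chemistry, hematology and urinalysis are "performed during screening (defined as baseline), on Day 0 and at 24 and 48 hours post each initial infusion". Section 6.5 uses the same label for supine blood pressure and continues: "respiratory rate and pulse will be recorded at screening (defined as baseline) and at Day 0". Coagulation is not named in the 6.7.1 sentence, and body temperature has its own sentence in 6.5 without the label. Section 6.5 also sets the ECG baseline at screening.

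**Timing.** Section 7.1.1 heads the screening visit: "To be accomplished within 15 days of expected initial dosing". The Synopsis (Study Design) uses a different anchor: "Screening must be within 15 days of subject enrollment".

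**Repeat on Day 0.** Section 7.1.2 and Table 12 place randomisation on Day 0, the day before the study starts, and repeat the laboratory panel there. For vital signs, 7.1.2 reads: "Perform vital sign and weight measurements". Table 12 shows no Day 0 ECG.

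**Analysis.** Section 10.3.1 plans a summary of changes in laboratory results without naming a reference visit. Section 10.3.2 says that the number and percentage of subjects with "laboratory abnormalities at the screening visit and the final visit (or early withdrawal) will be tabulated", and adds descriptive statistics by visit. Section 10.3 summarises vital signs by treatment group and specifies no change from baseline. Section 9.1.5 follows unexplained abnormal results until they are back in the normal range or at the baseline value, or are explained. Nothing in Section 10 redefines baseline.

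**The concern.** The usual reference for on-treatment change is the last value before treatment. Here the plan takes the older of two pre-dose values, although the newer one is collected at a scheduled visit.

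The patients have residual, recurrent or metastatic disease after failed chemotherapy, so values may move between screening and Day 0. Section 4.2 bars earlier cancer therapy only within 4 weeks of dosing. A screening sample 15 days before dosing could then be taken 28 - 15 = 13 days after the last treatment, while counts are still recovering. The Synopsis counts the 4 weeks back from screening, which would make this less likely. The two texts differ and need to be reconciled.

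Laboratory change matters in this programme. Section 1.5.2.3 attributes all four Phase 1b discontinuations for adverse events to anemia, and the two deaths to febrile neutropenia and pancytopenia. Section 1.5.2.15 asks for further verification of apparent falls in GGT and alkaline phosphatase. Confirming safety and tolerability is the secondary objective (Section 2.2).

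**Working it through.** **1. Are screening and Day 0 separate samples?** Table 11 lists laboratory draws at screening, Day 0, 24 and 48 hours in Weeks 1-4, and Week 6: 1 + 1 + 4 × 2 + 1 = 11 draws. At 14 mL each this is 11 × 14 = 154 mL, the total in the table. Day 0 is therefore a draw in its own right.

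**2. How much older is the named baseline?**
- Section 7.1.1: screening up to 15 days before dosing, Day 0 one day before. Extra age at most 15 - 1 = 14 days.
- Synopsis: up to 15 days before enrollment. If enrollment is taken as Day 0 (assumption), the extra age is at most 15 days.

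**3. What does the older reference do to change?** Let S, D and Y be the screening, Day 0 and post-dose values. Then

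Y - S = (Y - D) + (D - S).

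The term D - S arises wholly before treatment and enters every later change score for that patient. Likewise, an abnormality that appears between screening and Day 0 and persists would look like on-study onset in the 10.3.2 table. Both S and D precede the first infusion, and allocation is random on Day 0, so D - S has the same expectation in both arms. It cancels on average from the between-arm difference but remains in each arm's own mean change.

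**4. How much noise?** With equal variances σ² at each visit and correlation r between reference and post-dose value, Var(change) = 2(1 - r)σ². The documents give no r, so all values below are assumptions. Day 0 is held at r = 0.8, where Var(change) = 2 × 0.2 = 0.4σ². The standard error (SE) of the between-arm difference in mean change is √(2 × Var/11), with all 11 patients per arm measured. With the Day 0 baseline it is √(0.8/11) = 0.27σ.

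| r for screening | Var(change) | Ratio to Day 0 | SE of difference |
|---|---|---|---|
| 0.8 | 0.4σ² | 1.0 | √(0.8/11) = 0.27σ |
| 0.7 | 0.6σ² | 1.5 | √(1.2/11) = 0.33σ |
| 0.6 | 0.8σ² | 2.0 | √(1.6/11) = 0.38σ |

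**5. Does it persist?** Take the least favourable row, read 0.8 as the correlation at 1 day and 0.6 at 15 days, and let r decay exponentially: a factor 0.6/0.8 = 0.75 per 14 days (assumption). Day 1 of Week 6 is about 36 days after Day 0 and at most about 50 days after screening.
- Day 0: r = 0.8 × 0.75^(35/14) = 0.39
- Screening: r = 0.8 × 0.75^(49/14) = 0.29
- Ratio of variances: 0.708/0.610 = 1.16

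The penalty is thus largest soon after the first dose and small by the final visit.

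**6. Which analyses depend on it?** The laboratory change summary (10.3.1) names no visit, so the 6.7.1 label is the only definition it can draw on. The abnormality table (10.3.2) names screening itself. Vital signs have no stated change analysis. Mucositis is first scored on Day 0 (Table 12).

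**The case against.** A reader might infer that the screening baseline biases the comparison of TK-112690 with placebo. The documents do not support that: assignment is random and the drift precedes it, so both arms share it in expectation. What remains is a distorted within-arm change, added noise, and chance imbalance with 11 patients per arm. Chance imbalance of that kind exists with any baseline.

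A reader might also infer that the variance of change doubles. That is the upper end of an assumed range. It would apply at most to the earliest post-dose samples, with screening at the 15-day limit. If the two correlations are equal, nothing is lost.

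The affected analyses are few. Safety is summarised descriptively, no safety test is planned, and Section 10.1.1 calls the study exploratory. Section 10.3.2 gives statistics at applicable visits, so Day 0 values can still be displayed. The 4-week washout limits late effects of earlier therapy, though less so where it is counted back from dosing. No document shows that values really drift within the window.

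All of this stands and keeps the point small. None of it gives a reason to prefer the older value, and Section 10 does not override the label.

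**Conclusion.** The point holds as a minor, free improvement. Sections 6.5 and 6.7.1 name a baseline up to 14 days older than the Day 0 value (15 under the Synopsis wording, if enrollment means Day 0), and 10.3.2 uses the same visit. This misplaces pre-treatment shifts as on-study change within arms and adds noise between arms. The size is uncertain: a variance ratio of 1.0 to 2.0 at early visits under assumed correlations, and about 1.2 by Week 6 even in the least favourable case. No systematic between-arm bias is expected, and the mucositis results are not touched. The point does not extend to ECG, for which screening is the only scheduled pre-dose recording.

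**What to change.** - **Sections 6.5 and 6.7.1:** define the analysis baseline as the last non-missing value before the first infusion, normally Day 0, with screening as fallback. State whether coagulation, body temperature and weight follow the same rule.
- **Section 10.3.1:** name this baseline as the reference for the laboratory change summary.
- **Section 10.3.2:** use it in place of the screening visit in the table of abnormalities before treatment and at the final visit. Editing only 6.5 and 6.7.1 would leave this table inconsistent with them.
- **ECG:** leave the baseline at screening.
- **Section 9.1.5:** say which baseline value is meant. As this concerns follow-up of individual patients, the choice belongs to the clinical team.
- **Synopsis and Section 7.1.1:** reconcile the two anchors of the 15-day screening window.

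The cost is wording and table specifications only. No visit, sample or procedure is added.
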